7.7.3 Analysis of Exploratory Efficacy Endpoints

Durability of treatment effect will be examined in the DS for the exploratory efficacy endpoints. Additional sensitivity analyses of exploratory and secondary efficacy endpoints may also be conducted as exploratory analyses, including sensitivity analyses with regard to missing data. Further details of the exploratory analyses will be provided in the SAP.

7.7.4 Safety Analyses

All safety parameters (including AEs, vital signs, laboratory evaluations, SHBG, testosterone, and endometrial stripe thickness) will be summarized using the SA set. No formal hypothesis testing will be performed.

All AEs will be coded using the latest version of MedDRA. All TEAEs will be summarized and presented in the listings by the number of subjects reporting an event, the percentage of subjects with that event, the number of events, and the grade, duration, and relationship to treatment. Percentages will be based on the number of subjects who received each treatment during the study.

Clinical laboratory safety tests will be performed, and normal ranges will be provided for each laboratory test. Values outside the normal range will be assessed for clinical significance by the investigator. Shift tables (change from baseline value to on-treatment values) will be presented for each laboratory measurement and assessment time. Each parameter outside the normal range will be designated as high (H) or low (L) in the individual data listings.

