2.4 Safety Objectives

The safety objectives of this study are to determine the safety and tolerability of 2 doses of GTx-024 (1 mg and 3 mg administered once daily) compared to that of placebo therapy. Safety and tolerability will be assessed in relation to the following:

- Incidence of adverse events (AEs)
- Change from baseline in clinical laboratory evaluations
- Change from baseline in sex hormone binding globulin (SHBG) and testosterone
- Change from baseline in vital sign measurements
- Change from baseline in endometrial stripe thickness as assessed by transvaginal ultrasound (in subjects with an intact uterus)

3 Investigational Plan

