4.1.1 Inclusion Criteria

Each subject must meet all of the following criteria to be enrolled in this study:

1. Able to read, understand, and provide written, dated, informed consent prior to screening, and be likely to comply with study protocol and communicate with study personnel about AEs and other clinically important information.
2. Female, 18 to 80 years of age, inclusive, at screening
3. Subjects must have undergone spontaneous, medically induced, or surgical menopause prior to the start of this study. Postmenopausal subjects are defined as those subjects who meet one of the following criteria:
 - a) greater than or equal to 12 months of spontaneous amenorrhea, or;
 - b) at least 6 months of spontaneous amenorrhea with serum follicle stimulating hormone levels > 40 mIU/ml, or;
 - c) at least 6 weeks postsurgical bilateral oophorectomy with or without hysterectomy, or;
 - d) subjects 60 years of age or older with previous hysterectomy without an oophorectomy with serum follicle stimulating hormone levels > 30 mIU/ml, or;
 - e) subjects less than 60 years of age with previous hysterectomy without an oophorectomy with serum follicle stimulating hormone levels > 40 mIU/ml.
4. SUI symptoms of at least 6 months duration

5. Predominant SUI as determined at the Screening Visit using the MESA incontinence questionnaire.
6. 24-Hour pad weight > 3 g during the screening period
7. A minimum of 1 and no more than 15 SUI episodes on any single day AND no fewer than 9 total SUI episodes over 3 days as reported in the 3-day voiding diary, determined during the screening period
8. Serum alanine aminotransferase (ALT) or aspartate aminotransferase (AST) levels < 1.5 times the upper limit of normal at the Screening Visit (Note: laboratory values falling outside of prespecified ranges may be retested once at the discretion of the investigator. Results of the retest must be within prespecified ranges and must be available prior to the baseline visit)
9. Positive bladder stress test (BST) conducted during the Screening Visit
10. Subject agrees not to start any new treatment (medication or otherwise) during the treatment and follow-up periods, including vaginal rejuvenation, that is known or suspected to affect lower urinary tract function.
11. Subject agrees to discontinue use of bladder support devices, including but not limited to vaginal pessary, during the screening, treatment, and follow-up periods.

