6.3.3.6 Transvaginal Ultrasound

Only for subjects with an intact uterus, transvaginal ultrasound will be performed at screening and at the end of treatment (Visit 5) to observe changes in the endometrial stripe thickness (mm). Transvaginal ultrasound examinations will be evaluated locally.

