7.5 Analysis Sets

Data analysis will be performed on a full analysis set (FAS), a per protocol set (PPS), an intent-to-treat (ITT) set, a durability set (DS), and a safety analysis (SA) set.

The FAS is used for the primary analysis. The FAS consists of all randomized subjects who receive at least 1 dose of study drug and have at least 1 post baseline primary efficacy assessment (3-day voiding diary). All analyses using the FAS will group participants according to randomized treatment.

The PPS is used for a supportive analysis and will be defined as all subjects included in the FAS who do not have any significant protocol deviations. All analyses using the PPS will group subjects according to treatment actually received.

The ITT set consists of all randomized subjects who receive at least 1 dose of study drug. All analyses using the ITT set will group subjects according to randomized treatment. Subjects who do not have any postbaseline assessments will be treated as non-responders for ITT analyses.

The DS is used for exploratory analyses to assess the durability of the effect of treatment and will be defined as all subjects who complete a Week 12 final visit and a Week 16, Week 20, or Week 28 assessment.

The SA set contains all subjects randomized in the study who receive at least 1 dose of study drug. All analyses using the SA set will group subjects according to treatment actually received.

All efficacy analyses performed on the FAS will be repeated on the PPS and the ITT set. Further details will be provided in the SAP.

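### Percentages for strictly uterine and endometrial adverse events are divided by all treated women, including those without a uterus, and so understate the incidence in women at risk (minor)

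*Combined protocol and SAP*

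**What the plan says.** Section 7.7.4, repeated in the synopsis under Safety Analyses, states the rule for TEAE percentages: "Percentages will be based on the number of subjects who received each treatment during the study". No exception is made for any class of event. Section 7.5 defines the population without reference to uterine status: "The SA set contains all subjects randomized in the study who receive at least 1 dose of study drug". Safety is descriptive: "No formal hypothesis testing will be performed".

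Section 4.1.1, criterion 3, admits women without a uterus. Route (c) is "at least 6 weeks postsurgical bilateral oophorectomy with or without hysterectomy". Route (d) is for "subjects 60 years of age or older with previous hysterectomy without an oophorectomy" who meet a hormone threshold, and route (e) is its counterpart for women under 60. Nothing limits how many may enter this way, and section 5.1 mentions no stratification.

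Elsewhere the protocol recognises the at-risk group. The stripe-thickness objective (2.4), the ultrasound at screening and Visit 5 (6.3.3.6) and exclusion 17 (4.1.2) all apply only to women with an intact uterus.

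**The concern.** An incidence percentage should be taken over people who could have the event. A woman without a uterus cannot develop endometrial thickening or any other strictly uterine event, so counting her in the denominator lowers the percentage and adds no information.

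Such events can reach the adverse event tables under the protocol's own rules. Section 6.6 has clinically significant abnormal safety assessments recorded as adverse events, and 6.3.3 lists the transvaginal ultrasound among the safety assessments. Section 6.3.1.2 adds events identified from any study data. A significant ultrasound finding in a woman with a uterus then becomes a TEAE, and its denominator includes women who were never scanned.

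At stake is the absolute incidence that a reader takes from the table. Because safety is not tested formally, that printed percentage is the result.

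**Working it through.** **Arm size.** The only design figure needed is the number per arm, so I checked it first. Inputs from 7.4: 60% versus 40% response, two-sided 5%, 80% power, 25% discontinuation, 1:1:1 allocation.

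- n per arm = [1.960 × √(2 × 0.5 × 0.5) + 0.842 × √(0.6 × 0.4 + 0.4 × 0.6)]² / 0.20² = 96.9, so 97.
- Inflated for discontinuation: 97 / 0.75 = 129.3, so 130 per arm, or 390 in total.

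This agrees with the stated figure of approximately 400. I use 400 / 3 ≈ 133 treated per arm. The point does not dispute the sample size.

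**Dilution.** Let h be the share of an arm without a uterus, and x the number of women with a strictly uterine event.

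- Printed percentage = x / 133.
- Percentage in women at risk = x / [133 × (1 − h)].
- Printed / at-risk = 1 − h.

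The documents do not give h, so 10% to 50% is an assumed range. For an illustrative x = 5, the plan prints 5/133 = 3.76%:

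| Assumed h | Women at risk | At-risk percentage | Printed value too low by (relative) |
|---|---|---|---|
| 10% | 120 | 4.17% | 10% |
| 20% | 106 | 4.72% | 20% |
| 30% | 93 | 5.38% | 30% |
| 40% | 80 | 6.25% | 40% |
| 50% | 66 | 7.58% | 50% |

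If every enrolled woman has a uterus, h = 0 and there is no understatement.

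**Between arms.** Take illustrative at-risk rates of 5% on active and 2% on placebo.

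- h = 30% in both arms: the printed rates are 3.5% and 1.4%. The ratio stays at 3.5 / 1.4 = 2.5. The difference falls from 3.0 to 2.1 points, a factor of 0.7 = 1 − h.
- h = 35% on active and 25% on placebo: the printed rates are 5% × 0.65 = 3.25% and 2% × 0.75 = 1.50%, so the ratio is 2.17.
- The reverse imbalance: 3.75% and 1.30%, so the ratio is 2.88.

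At h = 30%, the chance SD of the between-arm difference in uterine status is √(2 × 0.7 × 0.3 / 133) = 5.6 points. A 10-point imbalance is therefore about 1.8 SD. It is possible but not typical, and equally likely in either direction.

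**The case against.** The strongest reply is that little of consequence depends on this sentence.

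- **A reader might infer that endometrial harm is a known risk being hidden.** The documents do not support that. Section 3.1.1.1 names ALT/AST elevation, HDL reduction and hypercalcemia, and no uterine or endometrial event.
- **A reader might infer that the endometrial safety objective is analysed wrongly.** It is not. That objective is the change in stripe thickness, which is continuous, restricted to women with an intact uterus, and independent of the TEAE denominator.
- **A reader might infer that the plan claims too tight a bound when no events are seen.** It states no such bound and plans no confidence limits for adverse events. A reader who worked out a one-sided 95% upper limit as 1 − 0.05^(1/n) would get 2.23% on n = 133, against 2.47% (n = 120) to 4.44% (n = 66) on women at risk. That would be the reader's calculation, not the plan's.
- **Not every gynecologic event is affected.** The diary records vaginal discharge and spotting in all subjects (6.2.1), and every subject has a pelvic examination at Visit 5 (6.4.1). Bleeding or spotting terms that do not require a uterus belong on the full denominator.
- **The at-risk number may be recoverable.** The baseline n in the stripe-thickness summary should approximate the intact-uterus count by arm, and 7.7.4 also reports event counts.
- **Sampling error is large.** The exact 95% interval for 4 events in 133 (3.0%) is 0.8% to 7.5%. Even at h = 50% the corrected 4/66 = 6.1% lies inside it.
- **Section 7.7 defers detailed methods to a separate SAP**, which is not in the text supplied and could contain an exception.

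Most of this stands and limits the weight of the point. It does not remove it. Sampling error is random, whereas the dilution always lowers the percentage. Readers should not have to rebuild a denominator from another table. The protocol's sentence is a stated rule without qualification, not a detail left open.

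**Conclusion.** The point holds for strictly uterine and endometrial terms only. For these, the stated rule gives (1 − h) times the incidence in women at risk. That is 10% to 50% too low in relative terms for an assumed h of 10% to 50%, and absolute differences between arms shrink by the same factor. The size rests wholly on h, which the documents do not give.

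It would be going too far to say that the comparison between arms is biased. Under randomization the ratio is unchanged in expectation, and chance imbalance in uterine status can only shift it one way or the other in a given trial. All other TEAE percentages, the stripe-thickness objective, and every test and power figure stand as they are. Severity: minor.

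**What to change.** In section 7.7.4 and the synopsis, keep the present sentence and add an exception: for strictly uterine and endometrial terms, percentages use treated subjects with an intact uterus at baseline. With it:

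- Fix the list of MedDRA terms before unblinding, so that the denominator is not chosen after results are seen.
- State that vaginal bleeding or spotting terms that can occur without a uterus stay on the all-treated denominator.
- Print the number of women with an intact uterus by arm in the adverse event tables.
- Carry the same rule into the SAP.

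Uterine status is available from the gynecologic surgical history taken at screening (6.3.3.4) and can be checked against who had the screening ultrasound (6.1.1.2). No new data, visits or subjects are needed. The cost is one added sentence, a short term list and one extra denominator. The small downside is that percentages for a few terms will look slightly less favourable.

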7.8 Data Quality Assurance

Standard operating procedures are available for all activities relevant to the quality of this study. Designated personnel will be responsible for implementing and maintaining quality assurance and quality control systems to ensure that the study is conducted and that data are generated, documented, and reported in compliance with the study protocol, Good Clinical Practice (GCP), and Good Laboratory Practice requirements as well as applicable regulatory requirements and local laws, rules, and regulations relating to the conduct of the clinical trial.

An authorized quality assurance auditor will audit the study data and procedures at periodic intervals as indicated. Domestic or foreign regulatory authorities, the IRB, and a Sponsor-authorized auditor may request access to all study documentation for an on-site inspection or audit. The Investigator must notify GTx, Inc. of any regulatory authority inspections and forward copies of the inspection report to GTx, Inc.

Electronic data systems will be in accordance with applicable aspects of 21 Code of Federal Regulations (CFR) Part 11, ICH Guidelines, GCP, local laws and legislation, and the Health Insurance Portability and Accountability Act.

7.8.1 On-Site Audits

At any time, quality assurance representatives of the Sponsor and/or regulatory bodies may visit the unit to carry out an audit of the study in compliance with regulatory guidelines and company policy. Such audits will require access to study records, documentation, and regulatory files. At all times, subject privacy will be of utmost importance and respected. Typically, sufficient notice will be given to the Investigator to prepare for the visit.

7.8.2 Data Management

As part of the responsibilities assumed by participating in the study, the investigator agrees to maintain adequate case histories for the subjects treated as part of the research under this protocol. The investigator agrees to maintain accurate eCRFs and source documentation as part of the case histories. Source documents may include, but are not restricted to, such documents as laboratory reports, ECG strips, and 3-day voiding diaries.

Investigative site personnel will enter subject data into InForm[®] (the eCRF program). The analysis data sets will be a combination of these data and data from other sources (e.g., laboratory data).

Clinical data management will be performed in accordance with applicable GTx standards and data cleaning procedures to ensure the integrity of the data, e.g., removing errors and inconsistencies in the data. Adverse events and concomitant medication terms will be coded using the MedDRA, an internal validated medication dictionary.

After database lock, each study site will receive a CDROM containing all of their site-specific eCRF data as entered into Oracle Clinical Remote Data Capture for the study, including full discrepancy and audit history. Additionally, a CDROM copy of all of the study site's data from the study will be created and sent to the Sponsor for storage. PPD will maintain a duplicate CDROM copy for their records. In all cases, subject initials will not be collected or transmitted to the Sponsor.

8 Ethics

8.1 Institutional Review Board

Federal regulations and the ICH guidelines require that approval be obtained from an IRB before participation of human subjects in research studies. Before study onset, the protocol, informed consent, advertisements to be used for the recruitment of study subjects, and any other written information regarding this study to be provided to the subject must be approved by the IRB. Documentation of all IRB approvals and of the IRB compliance with ICH harmonised tripartite guideline E6(R2): GCP will be maintained by the site and will be available for review by the Sponsor or its designee.

All IRB approvals should be signed by the IRB chairman or designee and must identify the IRB name and address, the clinical protocol by title or protocol number or both, and the date approval or a favorable opinion was granted.

The investigator is responsible for providing written summaries of the progress and status of the study at intervals not exceeding 1 year or otherwise specified by the IRB. The investigator must promptly supply the Sponsor or its designee, the IRB, and, where applicable, the institution, with written reports on any changes significantly affecting the conduct of the study or increasing the risk to subjects.

8.2 Ethical Conduct of the Study

The study will be performed in accordance with the ethical principles that have their origin in the Declaration of Helsinki, ICH GCP, and all applicable regulations.

8.3 Subject Information and Consent

A written informed consent in compliance with US Title 21 CFR Part 50 shall be obtained from each subject before entering the study or performing any unusual or nonroutine procedure that involves risk to the subject. An informed consent template may be provided by the Sponsor to investigative sites. If any institution-specific modifications to study-related procedures are proposed or made by the site, the consent should be reviewed by the Sponsor or its designee or both before IRB submission. Once reviewed, the consent will be submitted by the investigator to his or her IRB for review and approval before the start of the study. If

the ICF is revised during the course of the study, all active participating subjects must sign the revised form.

Before recruitment and enrollment, each prospective subject will be given a full explanation of the study and be allowed to read the approved ICF. Once the investigator is assured that the subject understands the implications of participating in the study, the subject will be asked to give consent to participate in the study by signing the ICF.

The investigator shall retain the signed original ICF(s) and give a copy of the signed original form to the subject.

9 Investigator's Obligations

The following administrative items are meant to guide the investigator in the conduct of the study but may be subject to change based on industry and government standard operating procedures, working practice documents, or guidelines. Changes will be reported to the IRB but will not result in protocol amendments.

9.1 Confidentiality

All laboratory specimens, evaluation forms, reports, and other records will be identified in a manner designed to maintain subject confidentiality. All records will be kept in a secure storage area with limited access. Clinical information will not be released without the written permission of the subject, except as necessary for monitoring and auditing by the Sponsor, its designee, the FDA, or the IRB.

The investigator and all employees and coworkers involved with this study may not disclose or use for any purpose other than performance of the study any data, record, or other unpublished, confidential information disclosed to those individuals for the purpose of the study. Prior written agreement from the Sponsor or its designee must be obtained for the disclosure of any said confidential information to other parties.

9.2 Financial Disclosure and Obligations

Investigators are required to provide financial disclosure information to allow the Sponsor to submit the complete and accurate certification or disclosure statements required under 21 CFR 54. In addition, the investigator must provide to the Sponsor a commitment to promptly update this information if any relevant changes occur during the course of the investigation and for 1 year following the completion of the study.

Neither the Sponsor nor PPD is financially responsible for further testing or treatment of any medical condition that may be detected during the screening process. In addition, in the absence of specific arrangements, neither the Sponsor nor PPD is financially responsible for further treatment of the subject's disease.

9.3 Investigator Documentation

Prior to beginning the study, the investigator will be asked to comply with ICH E6(R2) 8.2 and Title 21 of the CFR by providing the following essential documents, including but not limited to:

- IRB approval
- Original investigator-signed investigator agreement page of the protocol
- Form FDA 1572, fully executed, and all updates on a new fully executed Form FDA 1572
- Curriculum vitae for the investigator and each subinvestigator listed on Form FDA 1572
- Financial disclosure information to allow the Sponsor to submit complete and accurate certification or disclosure statements required under 21 CFR 54. In addition, the investigators must provide to the Sponsor a commitment to promptly update this information if any relevant changes occur during the course of the investigation and for 1 year after the completion of the study.
- IRB-approved informed consent, samples of site advertisements for recruitment for this study, and any other written information regarding this study that is to be provided to the subject
- Laboratory certifications and normal ranges for any local laboratories used by the site, in accordance with 42 CFR 493

9.4 Study Conduct

The investigator agrees that the study will be conducted according to the principles of ICH E6(R2). The investigator will conduct all aspects of this study in accordance with all national, state, and local laws or regulations. Study information from this protocol will be posted on publicly available clinical trial registers before enrollment of subjects begins.

